#### **9.2.4.2 Prespecified Biomarker Assessments**

Minimal residual disease in bone marrow is a mandatory measurement in this study.

Minimal residual disease will be measured by a NGS-based assay. Bone marrow aspirate sample will be collected as per Schedule of Activities ([Table 2-1](#)). The bone marrow aspirate sample will be processed and stored according to a protocol that is provided by the central lab. The samples will be analyzed centrally by the NGS-based MRD assay. See Section [9.2.2.2](#) for details on priority of samples for bone marrow aspirate testing.

#### **9.2.5 Pharmacokinetic Assessments**

All subjects enrolled will have pharmacokinetic (PK) samples assessed. Approximately 15 subjects in each arm will be invited to participate in the intensive PK/PDn substudy at select sites (see Section [9.2.9](#)). Sparse PK samples will be collected from the rest of the subjects, eg, subjects who do not consent to participate in the optional intensive PK/PDn substudy.

Venous samples of approximately 2.5 mL will be collected for measurement of plasma concentrations of carfilzomib as specified in the Schedule of Activities ([Table 2-1](#)).

Instructions for the collection and handling of biological samples will be provided by the sponsor. The actual date and time (24-hour clock time) of each sample will be recorded.

Samples will be collected within  $\pm$  5-minute time windows around the nominal time points (except for the time point immediately prior to the end of infusion, for which the PK collection needs to occur prior to the end of infusion).

#### **9.2.6 Pharmacodynamic Assessments (Only for Subjects Participating in the Optional Intensive PK/PDn Substudy)**

Venous blood samples of approximately 2 mL will be collected for measurement of carfilzomib PDn as per Schedule of Activities ([Table 2-1](#)). Blood samples will only be collected from approximately 15 subjects in each arm who consent to participate in optional intensive PK/PDn substudy (see Section [9.2.9](#)).

[figure not shown]
#### **9.2.7 Clinical Outcome Assessments**

All COAs will be completed via electronic tablet at the site prior to any other assessments or procedures.

##### **9.2.7.1 EORTC QLQ-C30**

[figure not shown]
The EORTC QLQ-C30 is a self-reported 30-item generic instrument for use in cancer subjects across tumor types. It assesses 15 domains consisting of 5 functional domains

(physical, role, emotional, cognitive, social), 9 symptom domains (fatigue, nausea and vomiting, pain, dyspnea, insomnia, appetite loss, constipation, diarrhea, financial difficulties), and a GHS or QOL scale (Aaronson et al, 1993).

#### **9.2.7.3        Patient-reported Convenience With Carfilzomib-dosing Schedule Question**

[figure not shown]
This is a carfilzomib-specific convenience single-item/question. This item was modified from a question used in the A.R.R.O.W. study (“neutral” option was removed). This item is not psychometrically validated (see Section [12.12](#) for more details).

#### **9.2.7.5        Cancer Therapy Satisfaction Questionnaire (CTSQ)**

The CTSQ measures treatment satisfaction in individuals with cancer (Trask et al, 2008). The CTSQ contains 3 domains covering 16 items (Cheung et al, 2016):

- Expectations of Therapy
- Feelings about side effects
- Satisfaction with therapy

### **9.2.9        Optional Substudies**

#### **9.2.9.1        Intensive Pharmacokinetic/Pharmacodynamic Substudy**

Approximately 15 subjects in each arm will be invited to participate in the intensive PK/PDn substudy at select sites. See Sections [9.2.5](#) and [9.2.6](#) for more details on the assessments.

Documentation of informed consent for the optional intensive PK/PDn substudy must be confirmed prior to performing intensive PK/PDn procedures.

### **9.2.10        Other Assessments**

Not applicable.

## **10.        Statistical Considerations**

### **10.1        Sample Size Determination**

The sample size was determined so that the primary objective could be tested via synthesis method at 1-sided 2.5% significance level with 80% power, including an interim analysis for futility when the first 230 subjects have been randomized and had the best overall response assessed by the date when treatment was completed, disease progression/death occurred, patient dropped out or started new therapy, whichever occurred first.

A sample size of 460 subjects is needed to achieve 80% power for demonstrating that once-weekly KRd 56 mg/m^2 preserves at least 60% of twice-weekly KRd 27 mg/m^2 effect in terms of ORR at a 1-sided 2.5% significance level by the synthesis method.

The stratified relative risk (RR) of ORR during the first 12 cycles of treatment in ASPIRE study (twice-weekly Rd vs KRd 27 mg/m^2 RR and 95% CI: 0.755 [0.696, 0.818]) will be used as the historical reference for the test of non-inferiority. This calculation assumes a true RR of 1 with ORR = 86.6% for both arms (once-weekly KRd 56 mg/m^2 vs twice-weekly KRd 27 mg/m^2), and an interim analysis for futility at 50% information fraction using O'Brien-Fleming beta-spending function. The reference ORR = 86.6% was determined based on the BOR observed by the end of 12 cycles of treatment in ASPIRE study (Amgen data on file).

## **10.2 Analysis Sets, Subgroups, and Covariates**

### **10.2.1 Analysis Sets**

The analysis and reporting of the data from this study will be performed using the following analysis populations:

#### **10.2.1.1 Intent-to-Treat Population**

The Intent-to-Treat (ITT) population constitutes all randomized subjects and will be the basis for the analyses of efficacy in this study. Subjects in the analyses based on the ITT population will be analyzed according to the treatment group to which they were randomized.

#### **10.2.1.2 Safety Population**

The safety population includes all randomized subjects who receive at least 1 dose of any study treatment (carfilzomib, lenalidomide, or dexamethasone), and will be the basis for the analyses of safety. Subjects in the analyses based on the safety population will be analyzed according to the treatment group corresponding to the actual treatment received. Any subject who received at least 1 weekly dose of carfilzomib 56 mg/m^2 will be included in arm 1 (once-weekly KRd 56 mg/m^2). Otherwise, subjects will be included in arm 2 (twice-weekly KRd 27 mg/m^2).

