#### **Organ Function Assessments**

- 229 Hepatic dysfunction within 28 days prior to randomization:
  - direct bilirubin  $\geq$  1.5x the upper limit of normal (ULN)
  - aspartate aminotransferase (AST) or alanine aminotransferase (ALT)  $\geq$  2.5 x ULN
- 230 Left ventricular ejection fraction < 40% assessed by transthoracic echocardiogram (ECHO).
- 231 Absolute neutrophil count (ANC) <  $1 \times 10^9/L$  within 28 days prior to randomization. Screening ANC should be independent of growth factor support for  $\geq$  1 week.
- 232 Hemoglobin < 80 g/L within 28 days prior to randomization. Use of erythropoietic stimulating factors and red blood cell (RBC) transfusions per institutional guidelines is allowed; however, most recent RBC transfusion must not have been performed within 7 days prior to obtaining screening hemoglobin.
- 233 Platelet count <  $50 \times 10^9/L$  ( $\leq 30 \times 10^9/L$  if myeloma involvement in the bone marrow is > 50%) within 28 days prior to randomization. Subjects should not have received platelet transfusions for at least 1 week prior to obtaining the screening platelet count.
- 244 Calculated or measured creatinine clearance < 30 mL/min (calculation must be based on the Cockcroft and Gault formula) within 28 days prior to randomization.

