**Arm 1 (once-weekly KRd 56 mg/m^2):**

Carfilzomib will be administered once-weekly IV as a 30 ± 5 minute infusion using an infusion pump on days 1, 8, and 15 of each 28-day cycle. The dose will be 20 mg/m^2 on day 1 of the first cycle and 56 mg/m^2 beginning with day 8 of cycle 1 and thereafter. All carfilzomib doses should be administered on the scheduled day ± 2 days, and the day 8 and 15 doses should have at least a 5-day treatment-free interval. Dose delays > 2 days are only permitted during the start of a new cycle.

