**Arm 2 (twice-weekly KRd 27 mg/m^2):**

Carfilzomib will be administered twice-weekly IV as a 10 minute ± 5 minute infusion using an infusion pump on days 1, 2, 8, 9, 15, and 16 of each 28-day cycle. The dose will be 20 mg/m^2 on days 1 and 2 of the first cycle and 27 mg/m^2 beginning with day 8 of cycle 1 and thereafter.

Every effort should be made to maintain the days 1, 2, 8, 9, 15, and 16 of 28-day schedule. If this is not possible, then priority should be to maintain consecutive dosing days. For example, if day 1 of a new cycle is started 2 days later than originally scheduled, the entire cycle should shift by 2 days, such that the new days 1, 2, 8, 9, 15, and 16 of the next cycle are maintained. There must always be at least 5 days between the second dose of 1 week and the first dose of the following week (ie, between days 2 and 8, and days 9 and 15). Mid-cycle doses that are missed should not be made up unless these parameters are maintained.

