#### **7.1.1.4 Starting Dose in Hepatic Insufficiency**

For subjects with baseline chronic hepatic impairment (mild, moderate), reduce the starting and subsequent doses of carfilzomib by 25% (Brown et al, 2017):

- for once-weekly arm: 15 mg/m^2 day 1 of cycle 1 and 42 mg/m^2 day 8 of cycle 1 and thereafter;
- for twice-weekly arm: 15 mg/m^2 day 1 and 2 of cycle 1 and 20 mg/m^2 day 8 of cycle 1 and thereafter.

If hepatic function returns to normal, the dose may be re-escalated to 56 mg/m^2 (for once-weekly arm) and 27 mg/m^2 (for twice-weekly arm) after the first cycle. For dose modification due to subsequent changes in hepatic function, refer to Section [7.4.1.1.2](#).

Mild and moderate hepatic dysfunction is defined as:

- Mild: 1.0 x ULN < bilirubin ≤ 1.5 x ULN; or AST > ULN with bilirubin ≤ ULN
- Moderate: 1.5 x ULN < bilirubin < 3 x ULN with any AST

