**Table 7-1. Dose Decremnts for Carfilzomib**

Nominal Dose (mg/m  )	Reduced Carfilzomib Doses (mg/m  )			
	Dose -1	Dose -2	Dose -3	Dose -4
20 a, b	15	11	Discontinue	-
27	20	15	11	Discontinue
56	45	36	27	20

a If dose reduction of carfilzomib is required on cycle 1 day 1 or cycle 1 day 2, the investigator should contact the medical monitor to discuss the situation before any additional doses of carfilzomib are administered.

b For subjects with baseline chronic hepatic impairment (mild, moderate), reduce the starting and subsequent doses of carfilzomib by 25% (ie, for once-weekly arm: 15 mg/m^2 day 1 of cycle 1 and 42 mg/m^2 day 8 of cycle 1 and thereafter; for twice-weekly arm: 15 mg/m^2 day 1 and 2 of cycle 1 and 20 mg/m^2 day 8 of cycle 1 and thereafter).

The subject will be considered on protocol treatment while receiving carfilzomib or lenalidomide.

If day 1 of a cycle is delayed, all subsequent doses within the cycle and also day 1 of subsequent cycles should be adjusted accordingly to maintain the 28-day cycle duration. However, if a within-cycle dose is delayed, then the dates of the subsequent within-cycle doses should not be adjusted. For within-cycle doses, if administration does not

commence within the allowable window of the scheduled administration date, then the dose will be considered a missed dose and this missed dose will not be made up. Administration may resume at the next planned dosing date.

If a subject requires interruption of carfilzomib for more than 6 consecutive weeks due to unresolved toxicities, the subject must be discontinued permanently from study treatment.

If a subject requires interruption of carfilzomib for more than 6 weeks for reasons other than toxicity, medical monitor approval is required prior to resuming treatment. The reason for dose change of carfilzomib is to be recorded on each subject's eCRF.

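### The protocol's safety-arm rule counts once-weekly subjects who never receive 56 mg/m² as twice-weekly, and the SAP omits the rule without replacing it

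*Protocol*

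**What the plan says.** Both documents admit to the safety set any randomized subject with one dose of any of the three drugs, and both say the subject is analysed by the treatment actually received (Protocol 10.2.1.2, SAP 6.2).

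Only the protocol turns this into a rule. "Any subject who received at least 1 weekly dose of carfilzomib 56" mg/m² is placed in arm 1. "Otherwise, subjects will be included in arm 2". SAP 6.2 stops at the principle. SAP section 5 defines no actual-treatment arm. SAP section 10 lists three departures from the protocol (restricted mean survival time, the observed retention rate and the ORR margin) and does not mention this one.

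The dosing text that matters is in Protocol 7.1.1.2 and 7.1.1.4:
- Once-weekly arm: 20 mg/m² "on day 1 of the first cycle and 56" mg/m² from day 8.
- Twice-weekly arm: 20 mg/m² "on days 1 and 2 of the first cycle and 27" mg/m² from day 8.
- Baseline chronic mild or moderate hepatic impairment: "reduce the starting and subsequent doses of carfilzomib by 25"%, which in the once-weekly arm gives 15 and then 42 mg/m². "If hepatic function returns to normal, the dose may be re-escalated to 56" mg/m², after the first cycle.

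**The concern.** The threshold sentence can contradict the sentence before it. A subject infused once a week at 42 mg/m² did not receive the twice-weekly regimen, yet the rule puts that subject in the twice-weekly arm. The same happens to a once-weekly subject who stops after the day 1 dose.

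The set is used for every safety analysis (SAP 9.6.1) and for exposure (SAP 9.6.8), and describing the safety of the once-weekly regimen is a stated purpose of the trial. Those moved include subjects who stop or die in the first week, so an early event on the new schedule would appear under the control. Because the SAP neither carries the rule nor replaces it, a programmer could defensibly follow either document.

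**Working it through.** The plan gives no figure on this point to reproduce, so the check is to apply the protocol rule to each dosing path the protocol allows.

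| Subject dosed as randomized | Arm under the Protocol 10.2.1.2 rule | Arm by schedule actually given |
|---|---|---|
| Once-weekly, reaches 56 mg/m² | 1 | 1 |
| Once-weekly, stops or dies before the first 56 mg/m² dose | 2 | 1 |
| Once-weekly, 15 then 42 mg/m², not re-escalated | 2 | 1 |
| Once-weekly, reduced before any 56 mg/m² dose | 2 | 1 |
| Once-weekly, lenalidomide or dexamethasone only | 2 | none; needs a default |
| Twice-weekly, any course | 2 | 2 (needs a default if no carfilzomib) |

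The movement is one-way because the scheduled twice-weekly doses are 20 and 27 mg/m², so correct dosing never triggers the arm 1 condition.

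**Are these paths realistic?** Early stopping needs no special circumstance. The hepatic path is narrow but open. Exclusion 229 ("Hepatic dysfunction within 28 days prior to randomization") removes AST or ALT at 2.5 × ULN or above, whereas 7.1.1.4 counts AST above ULN with bilirubin no higher than ULN as mild dysfunction. A subject between 1 and 2.5 × ULN is not excluded on AST and, if the impairment is chronic, follows the reduced schedule. The early-reduction path is narrowed by Table 7-1 footnote a: "If dose reduction of carfilzomib is required on cycle 1 day 1 or cycle 1 day 2", the medical monitor is contacted before further dosing.

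**Exposure tables** (doses from Protocol 7.1.1.4 and SAP Table 5-2, 12 cycles):
- Once-weekly plan: 20 + 35 × 56 = 1980 mg/m² over 36 doses.
- Twice-weekly plan: 40 + 35 × 54 = 1930 mg/m² over 72 doses, or 1930/72 = 26.8 per dose.
- Once-weekly on 15 then 42: 15 + 35 × 42 = 1485 mg/m² over 36 doses, or 1485/36 = 41.25 per dose.

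Such a subject would contribute 41.25 mg/m² per dose to an arm planned at 26.8. Relative dose intensity hardly moves. Actual weeks are (322 + 14)/7 = 48 and planned weeks are 4 × 11 + 4 = 48, so it is 1485/1980 = 75.0% against the once-weekly plan and 1485/1930 = 76.9% against the twice-weekly plan. For a subject with only the day 1 dose it is 20/20 = 100% against the once-weekly plan but 20/40 = 50% against the twice-weekly plan. The SAP does not say which plan applies to a subject analysed outside the randomized arm.

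**Event tables, illustration only.** Protocol 3.3.3.1.1 gives fatal cardiac failure as 0.8% on KRd in ASPIRE; 0.008 × 230 = 1.84, about 2 per arm. Assume 2 of 230 in each arm (0.87% each). The numbers moved below are assumptions.

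| Moved from once-weekly | Once-weekly shown | Twice-weekly shown |
|---|---|---|
| 1 subject, with the event | 1/229 = 0.44% | 3/231 = 1.30% |
| 5 subjects, 1 with the event | 1/225 = 0.44% | 3/235 = 1.28% |
| 5 subjects, none with the event | 2/225 = 0.89% | 2/235 = 0.85% |

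**The case against.** The strongest reply is that the SAP does not compete with the protocol. Its governing sentence is nearly the same, and SAP section 1 says that it details the analyses outlined in superseding protocol amendment 3. On that view the protocol rule remains in force and section 10 has nothing to list. It is correct that the SAP omits a rule and does not state a rival one, so a reader who infers two conflicting rules goes too far. But if the rule is inherited, its misclassification is inherited too; if it is not, there is no algorithm.

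A reader might also infer that the treatment actually received cannot be determined for a subject with only the day 1 dose, since that dose is 20 mg/m² in both arms. The documents do not support this. Planned infusion times are 30 ± 5 and 10 ± 5 minutes, ranges of 25–35 and 5–15 that do not overlap, and Protocol 7.1.1.2 has start and stop times recorded on the eCRF. Dose level alone does not identify the schedule, but the infusion record normally can. Only subjects with no carfilzomib are unclassifiable in principle.

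The threshold also has a merit: anyone exposed to a weekly 56 mg/m² dose, even by mistake, is counted with the new regimen. That argues against simply replacing it with the randomized arm, which would set aside a principle both documents share.

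Finally, some visibility is already planned. SAP 9.4 summarizes each analysis set by arm and lists the randomization, wrong-treatment deviations carry their own code (SAP 6.3) and are reported in the ITT set (SAP 9.3), and OS is analysed by randomized arm. A net shift in denominators would be noticed. These are partial checks: fatal and serious treatment-emergent events, causes of death and events of interest are tabulated only on the safety set.

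**Conclusion.** The point stands as a minor one. The protocol rule gives a wrong arm for identifiable groups of correctly treated once-weekly subjects, in one direction only, and the SAP leaves open whether that rule will be used.

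The size cannot be taken from the documents. The number moved is not given and is probably small: the hepatic and early-reduction groups are limited by eligibility, optional re-escalation and medical-monitor contact. The illustration shows no material effect unless a rare event falls in one of the few subjects moved. It also applies a whole-study rate from ASPIRE to subjects who mostly stopped within days, and the same section reports 1.0% on Rd, so it shows the mechanism and is not a forecast.

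A reader might infer that the safety comparison is biased in favour of the once-weekly regimen. That does not follow: moving subjects without the event slightly raises the once-weekly rate, and the direction depends on the event. ITT efficacy, OS, alpha and power are unaffected.

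**What to change.** In SAP 6.2, before database lock, state that:
- treated subjects are classified by the carfilzomib schedule actually given (once-weekly or twice-weekly), whatever dose level was reached and regardless of dose reductions, missed doses or early discontinuation;
- subjects who received no carfilzomib, or whose doses do not identify a schedule, are analysed in their randomized arm;
- subjects given the other arm's regimen in error are classified by the schedule they mainly received, and are listed.

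Record this in SAP section 10 as a change from Protocol 10.2.1.2, report the number of subjects whose safety arm differs from their randomized arm, and align Protocol 10.2.1.2 at its next amendment.

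The cost is one paragraph, one derivation rule and one count, with no new data. The trade-off is that a twice-weekly subject given a single 56 mg/m² dose in error would stay in arm 2; the listing keeps that exposure visible.

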#### **10.2.1.3 Per-Protocol Population**

The per-protocol population will include all randomized subjects who do not have any major protocol deviations that might affect the interpretation of the analyses of the efficacy endpoints. The major protocol deviations include:

- Major inclusion criteria not met
- Major exclusion criteria not met
- Major treatment non-compliance
  - Treatment received different from treatment randomized
  - Concomitant use of protocol prohibited medications.

### **10.2.2 Covariates**

In addition to the stratification factors for randomization (original ISS stage at study entry, prior lenalidomide treatment, prior PI treatment, prior anti-CD38 exposure), other baseline covariates may be considered to examine primary and selected secondary endpoints in subgroups or in sensitivity analyses, as appropriate. More details will be described in the statistical analysis plan (SAP).

### **10.2.3 Subgroups**

The ORR will be estimated for selected subgroups if appropriate:

- original ISS stage at baseline (stage 1 or 2 vs stage 3)
- prior lenalidomide treatment (yes vs no)
- prior PI treatment (yes vs no)
- prior anti-CD38 exposure (yes vs no)
- prior bortezomib treatment (yes, no)
- age (< 65, ≥ 65; 18 to < 65, 65 to < 75, ≥ 75)
- number of prior therapies (1 vs > 1; 1 vs 2 vs > 2)
- cytogenetic risk measured by FISH (high-risk vs standard risk)
- bortezomib refractory status (yes vs no)
- lenalidomide refractory status (yes vs no)
- prior transplant (yes vs no)

### **10.2.4 Handling of Missing and Incomplete Data**

Subjects may have missing data points for various reasons and the impact on the analysis might differ from 1 endpoint to another. The general rules for accommodating the missing or incomplete data may be refined during the blind review of the data, and they will be described in detail in SAP. Sensitivity analyses might be needed to evaluate the robustness of the primary analysis and/ or key secondary analyses results in case of significant missing data.

Incomplete dates for the start of adverse event, concomitant medications, and death will be imputed and the detailed rules will be specified in SAP.

The calculation of scores and methods to deal with missing data will be handled according to the EORTC QLQ-C30 questionnaire's standard scoring guidelines.

No imputation will be done for the analysis of the primary and key secondary endpoints. The frequency of missing disease assessments and deviation of the actual disease assessment times from the scheduled assessment times will be summarized by treatment arms. Sensitivity analyses will be performed to assess the impact of missing any disease or response assessment on the analysis of ORR and PFS. Similar analysis will be performed for QOL endpoints.

Details of missing data analysis and imputation rules will be described in SAP.

## **10.3 Statistical Analyses**

The SAP will be developed and finalized before database lock. Below is a summary of the timing and methods for the planned statistical analyses. To preserve study integrity, the final analysis will be conducted and reported following the end of study, as defined in Section 5.3.1.

### **10.3.1 Planned Analyses**

#### **10.3.1.1 Interim Analysis and Early Stopping Guidelines**

An interim futility analysis will be performed to limit the number of patients exposed to treatment in case of low activity.

The primary purpose of this interim analysis is to assess the likelihood that the treatment effect of the once-weekly KRd 56 mg/m^2 will preserve at least 60% of twice-weekly KRd 27 mg/m^2 effect in terms of ORR. The date of the analysis will be set up by Amgen based on the date when the first 230 subjects have been randomized and had a BOR assessed by the date when treatment was completed, confirmed PD or death occurred, subject was lost to follow-up, withdrew consent, or started new therapy, whichever occurred first.

This interim data analysis will address the primary and key secondary study objectives for the selected subjects. This analysis will be performed by an independent contract research organization, and the sponsor will be blinded to the results. An independent DMC will review the unblinded results and may suggest early termination of the trial. Using an O'Brien-Fleming beta-spending function, the stopping boundary for futility in p-value scale is 0.289. This stopping boundary corresponds to an approximate RR of 0.930, meaning that the study is futile if the observed ORR in the once-weekly KRd 56 mg/m^2 arm is < 80.8%, when the observed ORR in the twice-weekly KRd 27 mg/m^2 arm is 86.6%. With such a stopping boundary, the trial has over 70% probability to stop for futility when the null hypothesis of inferiority is true.

Based on this stopping criteria and clinical evaluation of the benefit/risk ratio, the DMC may recommend the continuation of study for the final analysis including all subjects enrolled in the study.

Data will be subject to ongoing checks for integrity, completeness, and accuracy in accordance with the Data Management Plan with the expectation that all outstanding data issues are resolved ahead of the snapshot. The data will be locked to prevent further changes, and a snapshot of the locked database will be used in the analysis.

